### 5.1 Objective(s)

---

The purpose of this registry is to observe the effects of Varithena® on VLU healing in patients who have the symptoms of chronic venous insufficiency. The objective of the registry is to evaluate VLU healing rate, recurrence rate, and patient reported outcomes for Varithena® in C6 disease per Clinical Etiologic Anatomic Pathophysiologic (CEAP) classification

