### 7.1.3 Post-treatment Management

Following treatment with Varithena®, subjects should be treated with compression dressing per Investigator's SoC. Subjects are referred to a local WCC. The WCC does not need to be affiliated with the investigational site. Subjects' compression dressing is checked and changed at the WCC. Subjects are asked to continue to visit the WCC weekly for continuing care until the wound is healed. At each WCC when the wound area is exposed, the patient should make every effort to take a photograph of the wound, or the wound area if the wound has healed, using the sDCT. The pain rating should also be recorded in the sDCT by response to the NPRS. The staff at the WCC are not delegated under the investigational site, so the subject should understand that they are responsible for collecting the photograph and answering the NPRS question independently.

If the wound is not healed at the 12 Week Follow-up visit, the subject continues to visit the WCC for continuing care until wound closure, collecting a wound photograph and answering the NPRS question at each appointment.

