#### **8.1.6 3 Months (±1wk) Post-Wound-Closure (Telephone)**

---

Once the subject's wound is determined to be healed, Tissue Analytics® schedules a reminder for Investigator or delegate to contact the subject by phone at 3 months (±1 week) to perform the following:

- Assessment for VLU recurrence
- Assessment of medical compression therapy compliance
- Request that subject collects the following using the sDCT:
  - Photograph of wound area, or wound if reoccurred
  - NPRS

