1.1 Study design

This 12 month, multicenter, open-label registry is designed to collect treatment and outcome data related to patients treated with Varithena® for great saphenous vein (GSV) system and/or anterior accessory saphenous vein (AASV) incompetence resulting in venous leg ulcer (VLU). Patients are treated per Investigator's standard of care (SoC) and in accordance with the full prescribing information (FPI) and instructions for use (IFU). For patients with healed ulcers during the 12 month follow-up period, VLU recurrence information is collected. Wound recurrence is defined as the reopening of a wound that was previously closed; all references throughout protocol to wound recurrence refers to wounds that are at the same location.

Note: In cases of cluster wounds, Investigator collects data for a single, primary wound. If more than one wound meets eligibility criteria, Investigator determines which wound to evaluate as the primary/target wound. All endpoint measurements are collected for the primary wound.

For each patient, participation in the registry lasts approximately 12 months. Patients are seen at the investigational site for initial treatment, about one week after treatment for initial follow-up visit (and retreatment if necessary), 12 weeks (± 1 wk) and 12 months (± 1 wk) after initial treatment. Between follow-up visits, and until wound closure, patients are asked to collect weekly photographs of the wound via the subject data capture tool (sDCT) during dressing changes at the wound care center (WCC).

Additionally, follow-up phone calls are placed at 3 months (± 1 wk) post-closure and 6 months (± 1 week) post-treatment. At that time, patients are asked to take a picture of the wound area and complete the numeric pain rating scale (NPRS) using the sDCT.

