3.3 Disposition, Demographics, Baseline

3.3.1 Disposition

Patient disposition will be summarized for all patients. The following categories will be summarized:

- Number of patients screened
- Number and percentage of patients in the efficacy population
- Number and percentage of bilateral patients (2 target wounds)
- Number and percentage of patients who discontinued
- Reasons for discontinuation
 - Withdrawn
 - Lost to follow-up
 - Death
 - Study discontinued by sponsor
 - Other
- Duration on study (months)
 - Duration (months) = (earlier date of study exit/death – date of first treatment + 1)/30.4375

Reasons for discontinuation and study exit dates are collected outside of the EDC. The reasons will be mapped into the categories above by clinical and provided to statistical programming for inclusion in summary table.

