3.5.1.3 Time to wound closure

Time to wound closure will be summarized by mean, median, standard deviation, quartiles, minimum and maximum. Additionally, the distribution of the time to wound closure will be analyzed by KM methodology. Any wound that was not closed will be censored at the last date on study. The 25th percentile, median and the 75th percentile will be presented along with the 95% CIs using the methodology of Brookmeyer and Crowley (1982)² using the log-log standard error. KM rates will be presented for each week with the corresponding 95% CIs using the log-log transformation methodology of Kalbfleisch and Prentice (1980)³. Plots of the KM curve will also be provided.

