3.5.2.6 Number of ulcer free weeks (time to recurrence)

The number of ulcer free weeks (time between healed wound and recurrence) will be summarized by mean, median, standard deviation, quartiles, minimum and maximum. If a patient's wound healed but did not have a recurrence, the patient will be censored at the last date of study. Additionally, the distribution of the time to recurrence will be analyzed by KM methodology. The 25th percentile, median and the 75th percentile will be presented along with the 95% CIs using the methodology of Brookmeyer and Crowley (1982)² using the log-log standard error. KM rates will be presented for each week through 12 weeks with the corresponding 95% CIs using the log-log transformation methodology of Kalbfleisch and Prentice (1980)³. Plots of the KM curve will also be provided.

Information for recurrence will be based on data from the EDC.

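### Tabulated Kaplan-Meier recurrence rates stop at week 12 after closure, so no censoring-adjusted rate is reported near the protocol's 6- and 12-month recurrence horizon

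*SAP*

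**What the plan says.** Recurrence is part of the registry's stated purpose. Protocol 5.1 says: "The objective of the registry is to evaluate VLU healing rate, recurrence rate", and continues with patient-reported outcomes. The protocol synopsis, 5.4 and 10.4 set the recurrence endpoint at 6 and 12 months post-treatment. A separate endpoint covers wounds still closed 3 months after closure.

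SAP 3.5.2.6 defines the time variable from closure: "The number of ulcer free weeks (time between healed wound and recurrence". Wounds without recurrence are censored at the last date on study. The planned outputs are summary statistics, KM quartiles with CIs, a KM plot, and this: "KM rates will be presented for each week through 12 weeks with the corresponding 95% CIs".

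The matching sentence for time to closure in SAP 3.5.1.3 has no limit: "KM rates will be presented for each week with the corresponding 95% CIs".

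Follow-up after closure is sparse. Protocol 7.1.3 says: "Subjects are asked to continue to visit the WCC weekly for continuing care until the wound is healed". The one contact timed from closure is the call in Protocol 8.1.6, where the site is to "contact the subject by phone at 3 months (±1 week) to perform the following". SAP 1.1 gives the same schedule: "follow-up phone calls are placed at 3 months (± 1 wk) post-closure and 6 months (± 1 week) post-treatment".

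SAP 3.5.2.2 reports the recurrence proportion as a single overall figure among healed wounds, with no time point attached.

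**The concern.** Twelve weeks is the natural horizon for healing, where the clock starts at treatment. In SAP 3.5.2.6 the clock starts at closure, and the SAP gives no reason for keeping the same limit. The printed rates therefore describe only the first 12 weeks of a closed wound, for an endpoint that the protocol places at 6 and 12 months post-treatment.

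This matters because wounds close at different times and so have unequal follow-up. A crude overall proportion mixes wounds watched for 48 weeks with wounds watched for a few. KM handles that, but its tabulated rates end before much of the follow-up is used. If the quartiles are not reached, the reader has no censoring-adjusted recurrence figure with a CI beyond week 12, only a plotted curve. Low early rates could then be quoted as the registry's recurrence result.

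**Working it through.** The documents state no recurrence assumption, event count or sample-size figure for this endpoint, so there is no plan figure to reproduce. The check has four parts.

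**1. Timing of the last tabulated rate**

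SAP 3.3.1 converts days to months with "date of first treatment + 1)/30.4375". On that basis:

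- 3 months = 3 × 30.4375 = 91.31 days; 91.31 / 7 = 13.04 weeks.
- The ±1 week call window is therefore weeks 12.04 to 14.04 after closure.
- The last tabulated rate is at 12 × 7 = 84 days = week 12.00, just before the window opens.
- If a site runs 3 months as 84 days, the window is weeks 11 to 13 and week 12 lies inside it.

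Other scheduled looks can come earlier. A wound closed at week 4 is photographed at the Week 12 visit (Protocol 8.1.5), 8 weeks after closure. The 6-month call (SAP 3.1 target day 183) is at 183 / 7 = 26.14 weeks. For wounds closing between week 26.14 − 12 = 14.14 and that call, it falls within 12 weeks of closure.

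**2. Assumed recurrence rates and the quartiles**

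Protocol 4.1 cites a randomised trial of superficial venous surgery plus compression against compression alone, with 12-month recurrence of 12% and 28%. I use these as a range, read as rates at 12 months after closure, with constant hazard. One year is 12 × 30.4375 / 7 = 52.18 weeks.

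- Hazard h = −ln(1 − r) / 52.18: 0.00245 per week at 12%; 0.00630 per week at 28%.
- Recurrence by week 12 = 1 − exp(−12h): 2.9% at 12%; 7.3% at 28%.
- 25th percentile = −ln(0.75) / h: week 117 at 12%; week 46 at 28%.
- Median = ln 2 / h: week 283 at 12%; week 110 at 28%.

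Follow-up runs 12 months from treatment (Protocol 7.1.4), so a wound closing at week c has 52.18 − c weeks after closure. At 12% no quartile is reached. At 28% the 25th percentile lies at the edge of follow-up: only wounds closing by about week 52.18 − 45.7 = 6.5 are watched that long.

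**3. Share of in-study recurrences after week 12**

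For closure at week c, share = 1 − F(12) / F(52.18 − c), with F(t) = 1 − exp(−ht).

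| Closure week | Weeks of follow-up | Share at 12% | Share at 28% |
|---|---|---|---|
| 8 | 44.2 | 72% | 70% |
| 12 | 40.2 | 69% | 67% |
| 20 | 32.2 | 62% | 60% |
| 28 | 24.2 | 50% | 49% |
| 40 | 12.2 | 1.5% | 1.4% |

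Averaging over exponential closure times with medians from 36 to 142 days gives 65-72% at 12% and 63-70% at 28%. Those two limits are mean healing times cited in Protocol 4.1, used here as medians.

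Sensitivity to the hazard shape: for a front-loaded Weibull hazard with closure at week 8 and one-year recurrence of 12% to 54%, the share is 51-59% at shape 0.7 and 39-46% at shape 0.5.

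**4. What later rows would show**

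With the same constant hazards, 1 − exp(−ht) at 13, 26 and 39 weeks is 3.1%, 6.2% and 9.1% at 12%, and 7.9%, 15.1% and 21.8% at 28%. Wounds still under follow-up at those times must have closed by weeks 52.18 − 13 = 39.2, 52.18 − 26 = 26.2 and 52.18 − 39 = 13.2.

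**The case against.** The strongest reply is that only the printed weekly rows are capped. SAP 3.5.2.6 also promises a KM plot with no stated cut-off, and quartiles over all follow-up. SAP 3.5.2.2 gives the overall proportion with a CI. SAP 3.5.2.1 gives the proportion still closed at 3 months and leaves out wounds that healed too late to be judged. SAP 3.4.1 summarises recurrence answers by visit. Protocol 10.4 planned no weekly rates at all, so the rows are an addition, in a descriptive registry with no hypotheses. All of this stands. It makes the point a reporting gap, not a failure to collect or analyse recurrence. It does not close the gap: the proportions are crude, and the plan promises neither CIs nor numbers at risk on the plot.

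The quartiles might also be reached. Protocol 4.1 quotes recurrence of 54-78% elsewhere, with no period given. If 54% were a one-year rate, constant hazard would put the 25th percentile near week 19. That is why the quartile statement is conditional.

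A reader might infer four stronger things that the documents do not support:

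- *The 3-month call is the first scheduled look after closure.* It is the only one timed from closure. The Week 12 visit or the 6-month call can come first, and Protocol 7.1.3 also asks for a photograph of the healed area at wound care visits.
- *The weekly rates may be the only KM result.* The plot is promised in the same section.
- *The table must show almost no recurrence by construction.* Recurrences can be found within 12 weeks, and the assumed rates give 2.9% or 7.3% by then.
- *Recurrences will be dated at the visit that finds them.* SAP 3.4.1 lists yes/no items only, but SAP 1.3 and Protocol 5.4 define the endpoint by a recurrence date, and the data-entry form is not available to settle it.

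**Conclusion.** The point holds as a gap in tabulated results. Censoring-adjusted recurrence rates with CIs stop at week 12 after closure. On the SAP's month length that is just before the closure-timed 3-month window; if 3 months is run as 84 days, it is inside it. On either reading it falls well short of the horizon the protocol set.

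Under constant hazard at 12% to 28% one-year recurrence, about 63-72% of in-study recurrences would fall outside the table. This rests on rates borrowed from a cited trial and on assumed closure times. The majority does not survive every assumption: it falls to about half for closure at week 28, and to 39-46% under the strongly front-loaded hazard. Even then a substantial share is untabulated. This is a modest, inexpensive improvement to a secondary endpoint that serves a stated objective.

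**What to change.** In SAP 3.5.2.6, replace the 12-week limit with KM recurrence estimates, 95% CIs and numbers at risk at 13, 26 and 39 weeks after closure. Print each row only while the number at risk is adequate, for example at least 10 wounds. The log-log interval method already named there can stay. These rows are on the post-closure clock, so they complement the protocol's 6- and 12-month post-treatment time points and do not replace them.

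Confirm whether the EDC records a recurrence onset date. Only if it does not would a sensitivity run be relevant, dating each recurrence at the midpoint between the last check showing closure and the check that found it.

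The cost is one amended sentence and a few table rows, with no new data. Later estimates will have wider intervals, most of all at 39 weeks, where only wounds closed by about week 13 still contribute.

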3.6 Additional Efficacy Analyses

A univariable cox regression model will be presented for the time to wound closure investigating effects of the following factors in a one at a time analysis: patient age, wound age at first encounter (weeks), presence of infection, ambulatory method, wound size at baseline and total wounds/ulcers of any type. The hazard ratio, 95% CI and the p-value will be summarized for each factor. All factors in the univariable models with a two-sided p-value <0.15 will be included in a multivariable analysis to determine the impact of these factors.

The overall VAS and change from baseline will be presented by summary statistics with 95% CI. Additionally, the EQ-5D-5L misery score will be calculated and summarized similarly to the VAS and index health state score. This is calculated by adding the dimensions together. As an example, if the health state is 11111, then misery score would be 5.

3.7 Safety analyses

The number of serious adverse events related to Varithena[®] will be listed.

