The AEs most commonly observed in the clinical studies of Varithena® are manageable events that would be expected in patients undergoing a minimally-invasive medical procedure for the treatment of GSV incompetence. These include infusion site thrombosis (retained coagulum), injection site hematoma, contusion, pain in extremity, limb discomfort, and superficial thrombophlebitis. Post-procedural pain resolved within 1 week in 80% of the cases reported, and very few Varithena®-treated patients were treated with opioid analgesics within 10 days of the study treatment procedure.

In the 1333 patients treated with Varithena® in the clinical studies, there were no anaphylaxis or major hypersensitivity reactions, no deaths or non-fatal SAEs attributed to the study treatment, and only a small number of patients with severe AEs or withdrawals due to AE. The following venous thrombus AEs occurred: common femoral vein thrombus extension (2.9%), proximal DVT (1.7%), distal DVT (1.1%), isolated gastrocnemius and soleal vein thrombosis (1.4%). Proximal symptomatic venous thrombi occurred in <1% of patients treated with Varithena®. Approximately half (49%) of patients with thrombi received treatment with anticoagulants.

Neurologic adverse events (e.g., cerebrovascular accident, migraines) have been reported in patients following administration of physician-compounded foam sclerosants. None of the 1333 patients in the Varithena® trials experienced clinically important neurological or visual adverse

events suggestive of cerebral gas embolism. The incidence of neurologic and visual adverse events within one day of treatment in the placebo-controlled studies was 2.7% in the pooled Varithena® group and 4.0% in the placebo groups.

Skin discoloration adverse events were reported in 1.1% of the pooled Varithena® group and 0.7% of the placebo group in the placebo-controlled studies.

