### Section 3. Adverse Events

**Continued on a separate sheet?**

Event No.	Adverse Event Term	Dates of Onset & Resolution (dd/mmm/yyyy)		Outcome of Event 	Causal Relationship 
1		Onset	/ /		
		Resolution	/ /		
2		Onset	/ /		
		Resolution	/ /		
3		Onset	/ /		
		Resolution	/ /		
4		Onset	/ /		
		Resolution	/ /		
5		Onset	/ /		
		Resolution	/ /		

(1) Outcome of Event (enter one code per event): 1 = Fatal 2 = Not Resolved 3 = Resolved 4 = Resolved with Sequelae 5 = Resolving  
(2) Causal Relationship to Varithena (enter one code): 0 = "Not related (no reasonable possibility)" 1 = "Related (reasonable possibility)"

**Section 4. Any relevant medical history/concurrent conditions and clinical progression of the adverse event including labs, diagnostics, etc.?**  Y  N *(If yes, specify below)*

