3.8 Interim analysis

An interim futility analysis will be performed when approximately 50 – 75 patients have enrolled and completed their 12 week post-treatment follow-up. The futility analysis will look for the following safety concerns:

- Hospitalizations due to target wound
- Serious adverse events related to Varithena[®]

If the analyses show there is a high safety concern, the study will be stopped.

Additionally, the descriptive summaries for the primary endpoints (see section 3.5.1 for further details on the primary endpoints) and the secondary endpoint of EQ-5D-5L (see section 0) and NPRS (see section 0) will be performed. Information on baseline wound characteristics (see section 3.3.2), treatment history (see section 3.4.1), post-treatment ultrasound and occlusion (see section 3.4.1) will be also be summarized.

4 Appendix

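### The SAP's adverse-event output, final and interim, shows only serious events judged related to Varithena, so it may say little about venous thrombosis

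*SAP*

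**What the plan says.** - **Final safety output.** SAP 3.7 is a single sentence: "The number of serious adverse events related to" Varithena will be listed. Protocol 10.7 plans no safety analysis.
- **Interim.** SAP 3.8 states that "The futility analysis will look for the following safety concerns". It then names two: "Hospitalizations due to target wound" and "Serious adverse events related to Varithena". The consequence is "If the analyses show there is a high safety concern, the study will be stopped", with no number attached.
- **Other SAP output.** SAP 3.4.1 summarizes whether and when a post-procedure duplex was done, vein occlusion, compression compliance, target-wound hospitalization and recurrence. No table or listing counts DVT, PE or extension of thrombus into the common femoral vein.
- **Population.** SAP 3.2 runs all analyses on the efficacy population. Treated patients who did not meet all eligibility criteria, or who lack a post-treatment primary endpoint assessment, are left out.
- **Earlier experience.** For 1333 treated patients, Protocol 4.3 reports "no deaths or non-fatal SAEs attributed to the study treatment". Beside this it gives thrombus rates of 2.9% (common femoral extension), 1.7% (proximal DVT), 1.1% (distal DVT) and 1.4% (calf muscle veins). It adds that about half of patients with thrombi were anticoagulated. Section 5.3 of the prescribing information (Protocol Appendix C) carries venous thrombosis as a warning.
- **Data collection.** Under Protocol 9.2 an investigator sends in an event if he or she wishes to report it. Appendix H takes the term, dates, outcome and a causality code for each event. As it reads in the public copy, it has no field for seriousness.

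**The concern.** The filter requires two judgements, seriousness and relatedness, before an event appears. In the sponsor's own earlier trials no event passed both, although thrombi of a kind the label warns about occurred and were often treated. The same could happen here: the final listing and the interim adverse-event count could be empty while thrombotic events sit on forms the sponsor already holds.

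The other interim input, hospitalization for the target wound, does not measure thrombosis. Protocol 12.8 gives the frequency or severity of adverse events as an example of a ground for ending the registry, but the interim output would not show either one across all reported events. Protocol 12.5 allows the data to support marketing, so a short or empty listing may be read as reassurance.

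**Working it through.** **1. Reproduce the earlier thrombus figures.**
- The prescribing information (section 6.1) gives 49% (n=35) anticoagulated. The sentence follows directly on a 0.9% figure for proximal symptomatic thrombi, but 0.009 x 1333 = 12 patients, fewer than 35. The 49% must therefore refer to all patients with thrombi, as Protocol 4.3 says.
- 35 / 0.49 = 71.4. Only denominators of 71 or 72 round to 49%. 71/1333 = 5.3% and 72/1333 = 5.4%. This patient count is inferred; the documents do not state it.
- Sum of categories: 2.9 + 1.7 + 1.1 + 1.4 = 7.1%, and 0.071 x 1333 = 94.6, about 95 events. This is an upper bound on patients, since one patient can fall in more than one category.

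**2. Check that 5-7% is not inflated for the 1% product.** The 1333 patients received 0.125% to 2.0%. In the label's Table 1 the 1.0% group had common femoral extension in 12/149 = 8.1% and DVT in 7/149 = 4.7%, against none of 151 on placebo. For VANISH-1, Protocol 4.3 gives 15 + 5 + 4 + 3 = 27 patients and 9.8%, which reproduces with a denominator near 275 (27/275 = 9.8%).

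**3. Expected thrombus events if ascertainment matched the earlier trials (n x rate).**

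| n | 5.4% | 7.1% | Proximal symptomatic only, 0.9% |
|---|---|---|---|
| 50 | 2.7 | 3.6 | 0.5 |
| 75 | 4.1 | 5.3 | 0.7 |
| 200 | 10.8 | 14.2 | 1.8 |

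At 5.4-7.1%, the chance of at least one event, 1 - (1 - p)^n, runs from 94% (n=50, 5.4%) to 99.6% (n=75, 7.1%) at the interim.

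**4. What the planned filter would show.** For 0 of 1333, the exact two-sided 95% upper limit is 1 - 0.025^(1/1333) = 0.28%. Even at that limit:
- 200 subjects: 200 x 0.00276 = 0.55 expected related serious events; chance of an empty listing (1 - 0.00276)^200 = 57%.
- 50-75 subjects: 0.14 to 0.21 expected; chance of none 87% to 81%.

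Step 4 assumes that seriousness and causality are judged as in the earlier trials. Step 3 assumes equal detection and reporting.

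**The case against.** The case on the other side is substantial.

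- **No safety conclusion is planned.** This is a registry of an approved product with healing, recurrence and patient-reported objectives. The SAP's safety output already goes beyond the protocol. A reader might infer that the safety conclusion will be wrong by construction. The documents do not support that: a listing titled as related serious events makes no claim about thrombosis. This stands.
- **A thrombosis can pass the filter.** Protocol 9.1 counts important medical events, including those that may need intervention, as serious. A DVT so classed and judged related would be listed. Protocol 4.3 does not say how seriousness was coded in the earlier trials, so the zero may not carry over. Hence the inference that thrombosis necessarily goes unreported is too strong. This stands.
- **There is oversight outside the SAP.** Forms go to the sponsor's vigilance function within 48 hours of awareness, Protocol 9.2 covers reporting to FDA, and the Protocol 12.8 termination ground is not limited to serious or related events. The interim also summarizes post-treatment ultrasound and occlusion. It would therefore be wrong to say that nobody would see a signal. The SAP's own outputs would still not count one.
- **Reports are incomplete by an unknown amount.** Reporting is voluntary and the Week 1 duplex is only as necessary (Protocol section 3, Table 1). A percentage with an exact confidence interval could show a falsely low rate. This stands, and it limits the fix to a listing and counts.

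Incomplete reporting is not a reason to remove, by a further filter, events that have been received.

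**Conclusion.** The point holds as one of reporting. SAP 3.7 and the adverse-event part of the SAP 3.8 stop are restricted to related serious events. In the sponsor's earlier data that restriction returned none of 1333, alongside thrombus events in about 5-7%. The output may be uninformative about a risk that the label carries as a warning.

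The size is about 11-14 events in 200 subjects and 3-5 in 50-75 if ascertainment matched the earlier trials. As a forecast of what will be reported, that is an upper scenario; proximal symptomatic thrombi alone would give about 2 in 200.

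Carrying rates over from a pool of mixed concentrations is an assumption. The pivotal trials excluded patients with a history of DVT or PE and those with reduced mobility, which the registry's listed exclusions do not name, so the underlying rate in this population could differ. The point does not show that any planned conclusion is wrong. The change is a worthwhile, inexpensive improvement.

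**What to change.** 1. In SAP 3.7, list all adverse events received on Appendix H, regardless of seriousness or causality, for all treated subjects and not only the efficacy population.
2. Give a separate count of reported venous thrombotic events by type: common femoral extension, proximal DVT, distal DVT, calf muscle vein thrombosis and PE.
3. Show the same listing and count at the SAP 3.8 interim, beside the related serious events. No stopping rule changes.
4. Label the counts as voluntarily reported events, a minimum and not an estimate of incidence. Omit the exact confidence interval, and give any percentage only with that caveat.

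The cost is SAP wording, one listing and one small count. No new data are collected. Verbatim terms on the forms will need some classification into the thrombotic types, and the reported safety profile will look less favourable than under the present filter.
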